7.1.3. Adverse Events of Special Interest

An AESI (serious or non-serious) is one of scientific and medical interest specific to the sponsor's product or program, for which ongoing monitoring and rapid communication by the investigator to the sponsor can be appropriate. Such an event might warrant further investigation in order to characterize and understand it. Depending on the nature of the event, rapid communication by the trial sponsor to other parties (eg, regulators) might also be warranted (Section 7.2.3).

7.2. Recording and Reporting Adverse Events

7.2.1. Adverse Events

The investigator (or designee) will seek information on AEs at each patient contact and record all AEs that occur from the time the informed consent is signed until 105 days (5 half-lives) after the end of study treatment. After informed consent has been obtained but prior to initiation of study treatment, only the following categories of AEs should be reported on the AE electronic CRF:

- SAEs
- Nonserious AEs associated with a protocol-mandated intervention (eg, AEs related to an invasive procedure such as a biopsy)

(Other AEs that occur prior to first treatment should be reported on the medical history CRF.)

All AEs after initiation of study treatment and until 105 days (5 half-lives) after the last study treatment, regardless of relationship to study treatment, will be reported on the AE electronic CRF. Additionally, any SAE or other AE of concern that the investigator believes may be related to study treatment and that occurs later than 105 days (5 half-lives) after last study treatment should be reported.

Information on follow-up for AEs is provided in Section 7.2.6. Laboratory, vital signs, or ECG abnormalities are to be recorded as AEs as outlined in Section 7.2.5.

Group 5 patients and Group 6 patients who opt to receive SC dosing only: any local ISRs will be reported as AEs in the CRF, as appropriate.

7.2.2. Serious Adverse Events

All SAEs, regardless of assessment of causal relationship to study treatment must be reported to the sponsor (or designee) within 24 hours. Refer to the safety reporting guidelines for the procedure to be followed.

Information not available at the time of the initial report must be documented in a follow-up report. Substantiating data such as relevant hospital or medical records and diagnostic test reports may also be requested.

In the event the investigator is informed of an SAE that occurs more than 105 days (5 half-lives) after the last dose of study treatment, only those SAEs or other AEs of concern deemed by the investigator to be related to study treatment will be reported to the sponsor. The investigator should make every effort to obtain follow-up information on the outcome of a treatment-related SAE until the event is considered resolved or chronic and/or stable.

7.2.3. Other Events that Require Accelerated Reporting to the Sponsor

The following events also require reporting to the sponsor (or designee) within 24 hours of learning of the event:

Symptomatic Overdose of Study Drug:

Accidental or intentional overdose of at least 2 times the intended dose of study drug within the intended therapeutic window, if associated with an AE.

Pregnancy:

Although pregnancy is not considered an AE, it is the responsibility of the investigator to report to the sponsor (or designee), within 24 hours of identification, any pregnancy occurring in a female patient or female partner of a male patient, during the study or within 105 days of the last dose of study drug. Any complication of pregnancy affecting a female study patient or female partner of a male study patient, and/or fetus and/or newborn must be reported as an SAE. Outcomes for all pregnancies should be reported to the sponsor.

Adverse Events of Special Interest:

An AESI must be reported within 24 hours of identification. Adverse events of special interest for this study include:

- Grade 2 or greater infusion-related reactions
- Grade 2 or greater allergic/hypersensitivity reactions
- Grade 3 or higher irAEs
- Grade 3 or greater ISR for the SC route
- An irAE of any grade in a patient previously treated with a PI 3-K inhibitor

Note: An irAE can occur shortly after the first dose or several months after the last dose of treatment. All AEs of unknown etiology associated with drug exposure should be evaluated to determine possible immune etiology. If an irAE is suspected, efforts should be made to rule out neoplastic, infectious, metabolic, toxin or other etiologic causes prior to labeling an AE as an irAE.

Refer to the safety reporting guidelines for the reporting procedures to be followed.

If any SAE or unusual AE is judged related to study treatment, and as possible and practical, obtain a blood sample from the patient to permit measurement of plasma drug levels.

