7. History of non-infectious pneumonitis within the last 5 years. If pneumonitis was purely infectious in etiology, enrolling on protocol may be allowed after discussion with medical monitor.
8. Grade ≥ 3 hypercalcemia at time of enrollment
9. Any systemic anticancer treatment (chemotherapy, targeted systemic therapy, photodynamic therapy), investigational or standard of care, within 30 days of the initial administration of cemiplimab or planned to occur during the study period (patients receiving bisphosphonates or denosumab are not excluded), radiation therapy within 14 days of initial administration of cemiplimab or planned to occur during the study period.
Note: For patients with multiple CSCCs at baseline that are not designated by the investigator as target lesions, treatment of these non-target CSCCs with surgery may be permitted but must be discussed with the medical monitor prior to any surgical procedure.
10. History of documented allergic reactions or acute hypersensitivity reaction attributed to antibody treatments.
11. Patients with allergy or hypersensitivity to cemiplimab or to any of the excipients must be excluded.
12. Breast feeding
13. Positive serum pregnancy test (a false positive pregnancy test, if demonstrated by serial measurements and negative ultrasound, will not be exclusionary, upon communication with and approval from the medical monitor).
14. Concurrent malignancy other than CSCC and/or history of malignancy other than CSCC within 3 years of date of first planned dose of cemiplimab, except for tumors with negligible risk of metastasis or death, such as adequately treated BCC of the skin, carcinoma in situ of the cervix, or ductal carcinoma in situ of the breast, or low-risk early stage prostate adenocarcinoma (T1-T2_aN0M0 and Gleason score ≤ 6 and PSA ≤ 10 ng/mL) for which the management plan is active surveillance, or prostate adenocarcinoma with biochemical-only recurrence with documented PSA doubling time of >12 months for which the management plan is active surveillance (D'Amico 2005, Pham 2016). Patients with hematologic malignancies (eg, chronic lymphocytic leukemia, CLL) are excluded.
15. Any acute or chronic psychiatric problems that, in the opinion of the investigator, make the patient ineligible for participation.
16. Continued sexual activity in men or women of childbearing potential (WOCBP)* who are unwilling to practice highly effective contraception prior to the initial dose/start of the first

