treatment, during the study, and for at least 6 months after the last dose. Highly effective contraceptive measures include:

- a. stable use of combined (estrogen and progestogen containing) hormonal contraception (oral, intravaginal, transdermal) or progestogen-only hormonal contraception (oral, injectable, implantable) associated with inhibition of ovulation initiated 2 or more menstrual cycles prior to screening
- b. intrauterine device (IUD); intrauterine hormone-releasing system (IUS);
- c. bilateral tubal ligation
- d. vasectomized partner (provided that the male vasectomized partner is the sole sexual partner of the WOCBP study participant and that the vasectomized partner has obtained medical assessment of surgical success for the procedure)
- e. and/or sexual abstinence^{†,‡}.

* WOCBP are defined as women who are fertile following menarche until becoming postmenopausal, unless permanently sterile. Permanent sterilization methods include hysterectomy, bilateral salpingectomy, and bilateral oophorectomy.

A postmenopausal state is defined as no menses for 12 months without an alternative medical cause. A high follicle stimulating hormone (FSH) level in the postmenopausal range may be used to confirm a postmenopausal state in women not using hormonal contraception or hormonal replacement therapy. However, in the absence of 12 months of amenorrhea, a single FSH measurement is insufficient to determine the occurrence of a postmenopausal state. The above definitions are according to Clinical Trial Facilitation Group (CTFG) guidance. Pregnancy testing and contraception are not required for women with documented hysterectomy or tubal ligation.

† Sexual abstinence is considered a highly effective method only if defined as refraining from heterosexual intercourse during the entire period of risk associated with the study drugs. The reliability of sexual abstinence needs to be evaluated in relation to the duration of the clinical trial and the preferred and usual lifestyle of the patient.

‡ Periodic abstinence (calendar, symptothermal, post-ovulation methods), withdrawal (coitus interruptus), spermicides only, and lactational amenorrhoea method (LAM) are not acceptable methods of contraception. Female condom and male condom should not be used together.

17. Patients with a history of solid organ transplant (patients with prior corneal transplant(s) may be allowed to enroll after discussion with and approval from the medical monitor).

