6.2.2. Follow-up

Patients who discontinue study treatment due to PD should return to the clinic 30 days (range: 21 to 42 days) after the last study treatment to complete the EOS assessments indicated in [Table 4](#) through [Table 9](#). After the EOS visit, patients should be followed for survival status until death, loss to follow-up, or study termination by the sponsor.

For all patients in Group 2, tumor biopsies ([Appendix 5](#)) should be obtained at time of progression, whether progression occurs in cycles 1 through 12 or during follow-up (after cycle 12).

Patients who discontinue study treatment due to reasons other than PD (eg, toxicity, confirmed CR after 48 weeks) should enter the follow-up schedule in [Table 9](#). (Note in clarification: Any patients who completed the posttreatment [Table 9](#) follow-up period of 6 months from previous amendments without disease progression will be asked to remain in follow-up. Such patients will be re-consented and asked to return approximately every 4 months (± 14 days) for 1 additional year to complete the extended follow-up assessments in [Table 9](#).)

For patients in Groups 1 or 2 who complete 12 cycles of treatment or for patients in Groups 3, 4, or 5 who complete 6 cycles of treatment without disease progression and subsequently experience disease progression during the follow-up period in [Table 9](#) without any intervening systemic anticancer therapy, resumption of treatment with cemiplimab 350 mg IV Q3W will be allowed. Prior to resumption of cemiplimab treatment, patients must be re-consented and repeat all screening activities (with the exception of providing new archived pathology material, or research biopsies), and the investigator must confirm that the patient still meets all eligibility criteria (other than the exclusion regarding prior treatment with anti-PD-1). Such patients will resume cemiplimab 350 mg IV Q3W for up to 108 weeks (maximum 12 retreatment cycles). The retreatment visit schedule will follow the study schedule in [Table 4](#). ADA samples will not be collected during retreatment. Patients in Group 5 who enter retreatment will not receive an additional dose of cemiplimab SC. For any patients who enter retreatment, the following are not required during retreatment: PK samples, research blood samples, and research tumor biopsies (exploratory tumor biopsies in Groups 2 and 4). *Note: Patients enrolled in Group 6 are not eligible for retreatment.*

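### The pregnancy-reporting window can close before the post-dose contraception window, most clearly for Group 6 patients who switch to SC dosing

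*Protocol*

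**What the plan says.** **Contraception.** Protocol 4.2.2, exclusion 16, keeps out sexually active men and women of childbearing potential who will not agree to reliable birth control. The obligation begins before dosing and then runs "during the study, and for at least 6 months after the last dose".

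**Pregnancy reporting.** Protocol 7.2.3 asks the investigator to notify the sponsor within 24 hours of any pregnancy in a female patient, or in a male patient's female partner, that occurs "during the study or within 105 days of the last dose of study drug". The same paragraph says that pregnancy is not itself an AE. It adds that complications are to be reported as SAEs and that all pregnancy outcomes should be reported; neither sentence carries a day limit.

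**AE reporting.** Section 7.2.1 collects AEs "until 105 days (5 half-lives) after the last study treatment, regardless of relationship to study treatment". After that, under 7.2.2, "only those SAEs or other AEs of concern deemed by the investigator to be related to study treatment will be reported to the sponsor".

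**How long patients stay in contact.**
- Completers and patients who stop for reasons other than progression follow Table 9. This has seven follow-up visits, each 28 ± 7 days after the one before.
- Group 6 patients who switch to SC dosing and complete Table 8 need only Follow-up 1 to 4. Table 9, footnote m, makes Follow-up 4 their last visit, describes it as more than 105 days after the last SC dose, and excludes them from survival follow-up.
- For progression, 6.2.2 says "Patients who discontinue study treatment due to PD should return to the clinic 30 days (range: 21 to 42 days) after the last study treatment" for the EOS assessments, and then "After the EOS visit, patients should be followed for survival status until death, loss to follow-up, or study termination by the sponsor".
- Under 4.3.3, patients who withdraw consent are not followed further.

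**The concern.** The protocol expects contraception for at least 6 months after the last dose, which implies that a conception in that period matters. The protocol does not call those months a risk window; that is an inference from the requirement. The reporting rule has two limbs: being on study, or being within 105 days of the last dose. Once a patient is no longer on study, only the second limb applies, and it ends about two and a half months before the contraception period does.

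The post-105-day AE rules do not fill the space. They reach only related SAEs and AEs of concern, and an uncomplicated pregnancy is not an AE. Routine testing does not fill it either, because Table 9 schedules a urine pregnancy test only at Follow-up 1 (and at progression, by footnote g). Later cases come to light mainly because a patient or partner tells the site, and the site then needs a clear written duty to pass the report on.

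At stake is the completeness of the fetal-exposure record. The ORR analysis is not touched.

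**Working it through.** **Inputs**

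| Input | Value | Source |
|---|---|---|
| Contraception after last dose | at least 6 months | Protocol 4.2.2, exclusion 16 |
| Reporting limit once off study | 105 days | Protocol 7.2.3 |
| Follow-up visit spacing | 28 ± 7 days | Protocol Table 9 |
| Last visit, SC switchers | Follow-up 4, no survival follow-up | Protocol Table 9, footnote m |
| EOS visit after progression | day 30 (21 to 42) | Protocol 6.2.2 |
| SC cycle | doses up to day 64 if three-weekly; end-of-cycle visit day 85 | Protocol Table 8, Appendix 3 |

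**1. The plan's own figure: Follow-up 4 falls more than 105 days after the last SC dose.** Table 9 counts from a final cycle visit.
- If that visit coincides with the last dose: 4 × 28 = 112 days.
- If it is the end-of-cycle visit on three-weekly dosing: 85 − 64 = 21 days after the last dose, so 112 + 21 = 133 days.

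Both exceed 105, so the figure reproduces at nominal timing. With every visit 7 days early the values are 4 × 21 = 84 and 84 + 21 = 105.

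**2. Difference between the two windows.** Six months = 6 × 365.25/12 = 182.6 days (181 to 184 by calendar).
- 182.6 − 105 = 77.6 days, range 181 − 105 = 76 to 184 − 105 = 79.
- As a share: 78/183 = 43%.

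This is the most that can be uncovered, and only for a patient who is off study by day 105.

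**3. What the study-period limb leaves uncovered**

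| Patients | Last contact that is clearly on study | Uncovered to day 182.6 |
|---|---|---|
| Complete Follow-up 1 to 7 | 7 × 28 = 196 days after the final cycle visit | none at nominal timing |
| Group 6 SC switchers, Table 8 completed | 112 days | 182.6 − 112 = 70.6 |
| Same, end-of-cycle anchor | 133 days | 182.6 − 133 = 49.6 |
| Same, all visits early | 84 or 105 days, so the 105-day limb governs | 77.6 |
| Progression, survival contact counted as on study | continuing | none |
| Progression, survival contact not counted | EOS visit, then the 105-day limb | 77.6 |

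Appendix 3 also lists a six-weekly SC schedule with dosing visits on days 1 and 43. Taking Table 8's 12-week cycle, an end-of-cycle anchor is 85 − 43 = 42 days after the last dose. Follow-up 4 is then at 112 + 42 = 154 days, with 182.6 − 154 = 28.6 days uncovered. The gap is shorter but still present.

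**The case against.** The strongest reply is that 105 days is not a cap. It is one side of an *or*, and the other side covers most patients. Section 3.1.2 puts the end of study for Groups 1 to 5 about 1.5 years after treatment. Section 6.2.2 gives patients in those groups who discontinue early four-monthly visits for a year and then quarterly contact. A patient followed for survival until the sponsor ends the study can naturally be regarded as still on it. Further, exclusion 16 is an eligibility condition on willingness, while 105 days is the protocol's general safety period of 5 half-lives, and nothing says that the two must match. The sentences on complications and outcomes have no day limit, and 7.2.3 defers procedures to safety reporting guidelines that are not available here.

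Much of this stands. A reader might infer that 43% of the contraception period has no reporting duty for patients in general. The documents do not support that: the gap is zero at nominal timing for those who complete Follow-up 1 to 7, and arguable for those in survival follow-up.

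Three things remain:
- SC switchers have neither visits nor survival contact after Follow-up 4. Section 3.1.2 places the end of study for Group 6 about 6 months after the follow-up period, which could be read to keep them on study. That general sentence is hard to square with footnote m, which is specific to them.
- The visit after progression is itself named End of Study, and no section says whether later survival contact counts.
- The sentences on complications and outcomes help only once a pregnancy has been recognised as reportable, and the related-only rule after day 105 may narrow the SAE route.

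**Conclusion.** The point holds, with limited reach, as a minor safety-reporting matter.

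- **Clear gap:** Group 6 patients who switch to SC dosing, planned at approximately 18 with more possible (Protocol 1.1.1). About 50 to 71 days of the 6-month contraception period have no stated reporting duty. This becomes about 29 days on the six-weekly schedule with an end-of-cycle anchor, or up to about 78 days if visits run early.
- **Ambiguous:** patients who stop for progression and have survival contact only. The gap is up to about 78 days if they are no longer on study, and none if they are.
- **No gap at nominal timing:** patients who complete Follow-up 1 to 7.

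This rests on a 6-month period of about 183 days, nominal visit dates except where stated, and reading Follow-up 4 as the end of participation for SC switchers. The documents give no count of patients or partners able to conceive. Few cases are expected, since the protocol's introduction describes CSCC as a disease of older patients. Efficacy conclusions are unaffected.

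**What to change.** Reconcile exclusion 16 and Section 7.2.3 so that the pregnancy-reporting window after the last dose equals whatever post-dose contraception window the protocol keeps. It should apply to female patients and to female partners of male patients, whether or not study visits have ended, subject to the consent-withdrawal rule in 4.3.3. Having 7.2.3 refer to the period in exclusion 16, rather than state its own number of days, would keep the two aligned through later amendments. Which duration is right is not judged here.

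The same edit should say whether survival-only contact counts as being on study, and should square the Group 6 end-of-study sentence in 3.1.2 with Table 9, footnote m.

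The cost is essentially a one-line amendment to 7.2.3 and a reminder to sites. It adds no visits or tests.

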7.2.4. Reporting Adverse Events Leading to Withdrawal from the Study

All AEs that lead to a patient's withdrawal from study treatment or from the study must be reported to the sponsor's medical monitor within 30 days.

Refer to the safety reporting guidelines for the procedures to be followed.

7.2.5. Abnormal Laboratory, Vital Signs, or Electrocardiogram Results

The criteria for determining whether an abnormal objective test finding should be reported as an AE include:

- the test result is associated with accompanying symptoms, and/or
- the test result requires additional diagnostic testing or medical/surgical intervention, and/or
- the test result leads to a change in dosing (outside of protocol-stipulated dose adjustments), and/or
- the test result leads to discontinuation from the study, significant additional concomitant medication, or other therapy

Contact the medical monitor in the event the investigator feels that an abnormal test finding should be reported as an AE, although it does not meet any of the above criteria.

Repeating an abnormal test, in the absence of any of the above conditions, does not constitute an AE. Any abnormal test result that is determined to be an error does not require reporting as an AE.

Evaluation of severity of laboratory abnormalities will be assessed according to the scale outlined in Section 7.3.1.

7.2.6. Follow-up

Information for any nonserious AE that starts during the treatment period or within 105 days (5 half-lives) after last treatment will be collected from the time of the event until resolution of the event, or until the patient's last study visit, whichever comes first.

Serious adverse event information will be collected until the event is considered resolved or chronic and/or stable.

7.3. Evaluation of Severity and Causality

7.3.1. Evaluation of Severity

The severity of AEs (including test findings classified as AEs) will be graded using the current version of the NCI-CTCAE grading system. Adverse events not listed in the NCI-CTCAE will be graded according to the following scale:

- | | |
|----------------------|---|
| 1 (Mild): | Mild; asymptomatic or mild symptoms; clinical or diagnostic observations only; intervention not indicated. |
| 2 (Moderate): | Moderate; minimal, local or noninvasive intervention indicated; limiting age-appropriate instrumental ADL*. |

- 3 (Severe):** Severe or medically significant but not immediately life-threatening; hospitalization or prolongation of hospitalization indicated; disabling; limiting self-care ADL**.
- 4 (Life-threatening):** Life-threatening consequences; urgent intervention indicated.
- 5 (Death):** Death related to AE

* Instrumental Activities of Daily Living (ADL) refer to preparing meals, shopping for groceries or clothes, using the telephone, managing money, etc.

** Self-care ADL refer to bathing, dressing and undressing, feeding self, using the toilet, taking medications, and not bedridden.

The grading criteria for ISRs in Section 5.4.3 are different than NCI-CTCAE version 4.03 grading of ISRs, because the criteria in Section 5.4.3 are more descriptive of potential local reactions to this class of drug.

